## **7 Statistical considerations**

### **7.1 Standard descriptive statistics**

The data of continuous type will be presented with following statistics:  $n$  (the number of subjects with non-missing data), mean, median, standard deviation (SD), interquartile range (IQR), minimum and maximum values. In quantitative tests the values less than LLoQ will be replaced to 1/2 of LLoQ, the values more than ULoQ will be replaced to ULoQ.

The data of categorical type (including clinical evaluations) will be presented with  $n$  (the number of subjects with no missing data), frequencies and percentages. Unless otherwise specified, percentages by categories will be based on the number of subjects with no missing data.

Confidence intervals will be calculated for all effectiveness endpoints and questionnaires results.

The number of decimals for each descriptive statistical value will be determined by the following rules:

- mean, median and IQR: +1 decimal place compared to the analyzed variable values;
- standard deviation: +2 decimal places compared to the analyzed variable values;
- minimum and maximum values: the same as for the analyzed variable values;
- percentages (including CI) will be rounded to one decimal place.

The maximum number of decimal places in the statistical report is four. If some descriptive statistical value has more than four decimal places after above mentioned rules application, this value will be rounded to four decimal places .

### **7.2 Statistical tests and common calculations**

Unless otherwise specified in the description of the analyses, the following arrangements will be applied:

- all tests will be two-sided with the default significant level 5%;
- confidence intervals will be 95% and will be determined using the Clopper-Pearson method.

Type I error values (p-values) will be rounded to four decimal symbols.

For quantitative measurements of clinical laboratory data, changes from baseline will be calculated as (measurement at visit X – measurement at baseline).

### **7.3 Missing Data**

No data will be imputed for any effectiveness or safety analyses.

If information about adverse event start date and time is missing or incomplete, the following rules (table 7.1) will be used for the classification of AEs for AEs of the study period and AEs, which occurred before the start of treatment.

Table 7.1 – AEs missing management.

| Day        | Month      | Year       | Processing   |
|------------|------------|------------|--|
| is missing | is known   | is known   | AE will be classified as AE of the study period, if month and year $\geq$ month and year of the first study drug administration date |
| is missing | is missing | is known   | AE will be classified as AE of the study period, if year $\geq$ year of the first study drug administration date                     |
| is known   | is missing | is known   |  |
| is missing | is known   | is missing | AE will be classified as AE of the study period  |
| is known   | is missing | is missing |  |
| is missing | is missing | is missing |  |

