In accordance with the non-interventional nature of the study all HCV RNA measurements will be performed at the sole discretion of the physician and all HCV RNA measurements have to be entered into the eCRF. All recorded HCV RNA values will be assigned to appropriate time points (baseline, on-treatment visits, EoT visit, post-treatment visits). The time windows for the assignments will be specified in the statistical analysis plan (SAP).

No data will be imputed for any effectiveness or safety analyses except for the analyses of the HCV RNA endpoints. When there is no HCV RNA value in a visit time window post-baseline, but prior to EoT, the closest values before and after the window, regardless of the value chosen for the subsequent and preceding window, will be used for the flanking imputation described below. If a patient has a missing HCV RNA value at a post-baseline visit prior to EoT but has undetectable HCV RNA (with LLoD ≤ 50 IU/mL) or unquantifiable, but detectable HCV RNA levels (with LLoQ ≤ 50 IU/mL) at both the preceding and succeeding measurements, the HCV RNA level will be considered undetectable or unquantifiable, respectively, at this visit for this patient. In addition, if a patient has an unquantifiable HCV RNA level at the preceding measurement and an

Confidential Information

No use or disclose outside AbbVie is permitted without prior written authorization from AbbVie

Version 3.0 (22 Apr 2015) – country v 1.0 dated 26.06.2015

Page 33 of 61

undetectable HCV RNA level at the succeeding measurement, or vice versa, the HCV RNA level will be imputed as unquantifiable at this visit for this patient. For virological response at EoT a corresponding backward imputation approach will be applied. This means if HCV RNA is missing at EoT, then unquantifiable or undetectable will be assumed for EoT, if the succeeding HCV RNA value is undetectable or unquantifiable. For SVR12 the single last available HCV RNA measurement ≥ 70 days post-treatment will be used. Subsequent to this flanking and backward imputation, if the HCV RNA value remains missing at a specific time point, then the patients will be considered as virological failure at this time point (i.e. not undetectable or unquantifiable).

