9.7.3 Effectiveness Analysis

The primary effectiveness analysis on clinical outcomes will be performed on all patients in the CP stratified by the CP analysis groups. Due to the non-interventional nature of this study several different methods for determination of the HCV RNA value can be applied. For the purpose of the statistical analysis, a HCV RNA measurement is considered ≤ 50 IU/mL,

- if a PCR test was used
- and the test result is undetectable and the LLoD of the test is ≤ 50 IU/mL or the test result is unquantifiable and the LLoQ is ≤ 50 IU/mL

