## 9 Effectiveness analysis

Effectiveness analysis will be conducted on *the core population (CP)*, *the target population (TP)* and *the core population with sufficient follow-up data (CPSFU)*.

The results will be reported overall and for scheduled treatment combination ( $\pm$  RBV) and duration (12 or 24 weeks) groups. Additionally and only for *the core population (CP)* the results will be presented for the CP analysis groups by the following parameters:

- HCV genotype and subtype (1a or 1b);
- fibrosis status (the Child Pugh Score class: A, B or C);
- treatment experienced or naïve patients (with/without prior treatment for CHC).

Tables with descriptive statistics will be prepared in accordance with section 7.1. Confidence intervals will be presented according the section 7.2. All corresponding listings will be presented. Additional listings for *the non-core population (NCP)* will be created.

The following effectiveness endpoints will be analyzed:

- the percentage of patients achieving SVR12 (single last HCV RNA <50 IU/mL 12 weeks after the last actual dose of the ABBVIE REGIMEN);
- the percentage of patients with at least one and each of SVR12 non-response categories:
  - breakthrough (at least one documented HCV RNA <50 IU/mL followed by HCV RNA  $\geq$ 50 IU/mL during treatment);
  - failure to suppress (each measured on-treatment HCV RNA value  $\geq$ 50 IU/mL);

---

 Parameter “HCV Genotype and Subtype” from eCRF form “CHC DISEASE CHARACTERISTICS”.

 Parameter “Class” in section “Child Pugh Score” from eCRF form “Liver fibrosis stage”.

 Parameter “Prior treatment for CHC?” from eCRF form “MOST RECENT PRIOR THERAPY FOR CHC”.

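### SAP 7.3 omits the protocol's HCV RNA exception on missing data, so end-of-treatment response departs from the supplied protocol on either reading of the SAP

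*SAP*

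**What the plan says.** Protocol 9.7.1 (supplied version 3.0, country version 1.0) reads: "No data will be imputed for any effectiveness or safety analyses except for the analyses of the HCV RNA endpoints". Three rules follow for those endpoints:

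- Before EoT, neighbouring values "will be used for the flanking imputation described below".
- At EoT, provided the next value is undetectable or unquantifiable: "if HCV RNA is missing at EoT, then unquantifiable or undetectable will be assumed for EoT".
- After that, "if the HCV RNA value remains missing at a specific time point, then the patients will be considered as virological failure".

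Protocol 9.7.3 fixes the primary set: "The primary effectiveness analysis on clinical outcomes will be performed on all patients in the CP stratified by the CP analysis groups".

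SAP 7.3 keeps only the first half of the protocol sentence: "No data will be imputed for any effectiveness or safety analyses". None of the three rules appears elsewhere in the SAP. SAP 16 declares the methods wholly consistent with the protocol and reports one change, the dropped regression for the patient support program.

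On denominators, SAP 7.1 sets a default: "Unless otherwise specified, percentages by categories will be based on the number of subjects with no missing data". SAP 9 brings it into the effectiveness section: "Tables with descriptive statistics will be prepared in accordance with section 7.1". SAP 9 and Table 2.1.1.1.1 list missing SVR12 as a non-response category. EoT response and SVR24 have no such category. The table's footnotes define N as the core population (CP) and do not state the percentage denominator. Table 2.1.1.1.3 repeats the layout without patients whose SVR12 is missing, yet its footnote still gives N as the CP.

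**The concern.** HCV RNA testing is at the physician's discretion in this study, and Protocol 9.9 names missing HCV RNA as a main threat to interpretation. The missing-data rule therefore helps determine the reported rates.

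Without the exception, a programmer has no instruction for a patient with no EoT value. That patient may have a negative result some weeks later, which the protocol would carry back to EoT. At stake are the EoT response rate, which is a listed secondary endpoint and also a logistic-regression outcome in SAP 9, and to a lesser degree the SVR24 rate. Because SAP 16 reports no such change, a reader of the results would assume that the protocol's rule had been applied.

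**Working it through.** **Reference figure.** The planned size is 158 evaluable patients at an expected SVR12 of 90%, with an exact interval of 84.2% to 94.2%. A two-sided 95% Clopper-Pearson interval with n = 158 and x = 0.9 × 158 = 142.2 gives 84.23% to 94.20%, width 9.97 points. The figure reproduces and is not in dispute; 158 serves below as the illustrative CP size.

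**EoT response: formulas.** Let N be the CP, o the patients with an EoT value, r the responders among them, u = N − o the untested, and b the untested patients with a later qualifying negative result.

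- SAP 7.1 default: r / o
- n/N without imputation: r / N
- Protocol 9.7.1: (r + b) / N

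The n/N reading falls short of the protocol by b/N and agrees with it only when b = 0. The 7.1 reading exceeds the protocol whenever b < r × u / o.

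**EoT response: numbers.** The documents give no missing-data rate, so these inputs are assumed: N = 158, 155 true responders, the 3 non-responders all tested, and 16 responders untested. Then o = 142 and r = 139. The 7.1 default gives 139/142 = 97.9% (95% CI 94.0 to 99.6). The n/N reading gives 139/158 = 88.0% (81.9 to 92.6).

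| Back-filled (b) | Protocol rule | 7.1 minus protocol | n/N minus protocol |
|---|---|---|---|
| 16 | 155/158 = 98.1% | −0.2 | −16/158 = −10.1 |
| 14 | 153/158 = 96.8% | +1.1 | −14/158 = −8.9 |
| 8 | 147/158 = 93.0% | +4.8 | −8/158 = −5.1 |
| 0 | 139/158 = 88.0% | +9.9 | 0 |

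The crossing point for the 7.1 reading is 139 × 16/142 = 15.7, so here it overstates unless all 16 are back-filled.

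With 8 responders untested, 7.1 gives 147/150 = 98.0% and n/N gives 147/158 = 93.0%. The protocol rule gives 98.1% with all 8 back-filled, 151/158 = 95.6% with 4, and 93.0% with none.

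**SVR24.** The protocol sets no imputation after EoT, so its general sentence on remaining missing values makes an untested patient a failure. Under n/N that patient is not counted as a responder, which gives the same rate. Only the 7.1 reading differs. With 4, 8 or 16 missing and about 90% response among those tested:

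- 139/154 = 90.3% against 139/158 = 88.0%, gap 2.3 points
- 135/150 = 90.0% against 135/158 = 85.4%, gap 4.6 points
- 128/142 = 90.1% against 128/158 = 81.0%, gap 9.1 points

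**SVR12.** Table 2.1.1.1.1 counts missing as non-response, so the protocol's final rule survives there. The same arithmetic gives the gap between Tables 2.1.1.1.1 and 2.1.1.1.3. It is zero if no SVR12 result is missing, and the second table can never show the lower rate.

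**Flanking imputation.** It fills visits before EoT. The SAP reports no response rate at those visits; breakthrough needs a documented value and failure to suppress uses measured values. Its loss changes no listed endpoint.

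**The case against.** The strongest reply is that the shells point to n/N. Table 2.1.1.1.1 has a single N, no row of valid measurements, and an n defined as subjects in a category. Tables 1.2 and 1.3 describe n the same way and state the percentage as 100 × n/N. SVR12 in the same table needs the full CP, and a separate table without missing SVR12 makes sense only if the first table keeps those patients. This stands: the available-case result is one of two defensible readings. It does not rescue EoT, because n/N without back-filling also departs from the protocol.

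Second, the shell footnotes say that the CP and the core population with sufficient follow-up data contain the same subjects, although the later table list treats this as conditional. If they are the same, few responders lack a later result, and the +9.9-point case is unlikely. This also stands. It moves the 7.1 reading close to the protocol rule, but it makes the n/N shortfall larger, since most untested patients would then qualify for back-filling.

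Third, SAP 2 cites protocol 4.0. A reader might infer that the sponsor silently altered an agreed rule. The documents do not show this: version 4.0 may have removed the exception deliberately.

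A reader might also infer from the label main analysis on Table 2.1.1.1.3 that the table excluding missing SVR12 is the primary one. It is not shown to be. In SAP 9 that label separates the <50 IU/mL definition from the additional one that accepts undetectable or negative results, and Protocol 9.7.3 points to all CP patients.

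**Conclusion.** The point holds for EoT response, measured against the supplied protocol. SAP 7.3 omits the HCV RNA exception. Under the 7.1 default, untested patients leave the denominator. Under n/N, untested patients with a later qualifying negative result become failures. Neither is the protocol's rule, and they coincide with it only in special cases.

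In the 16-untested illustration, the rates are 97.9% and 88.0% against 98.1% (all back-filled) or 96.8% (14 back-filled). Larger gaps between 7.1 and the protocol rule need many patients with no later qualifying result. All sizes rest on assumed missingness, and the real effect may be small.

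For SVR24, which is an effectiveness endpoint in the SAP but not in the protocol, the finding is an ambiguous denominator; only the 7.1 reading departs from missing = failure. For SVR12, what remains is a footnote in Table 2.1.1.1.3 that contradicts its title, and no statement of which table is primary. The wider inference that the primary SVR12 analysis has become available-case is not supported.

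**What to change.** 1. In SAP 7.3, restore the HCV RNA exception: backward imputation at EoT, then remaining missing = failure. Flanking imputation may be restored for consistency. If protocol 4.0 removed the exception, record and justify that in SAP 16.
2. In SAP 9, state that SVR12, EoT and SVR24 percentages use all patients in the analysis population, overriding SAP 7.1.
3. Name Table 2.1.1.1.1 as the primary analysis and label Table 2.1.1.1.3 as a sensitivity analysis. Correct the latter's N footnote to CP patients with an SVR12 result.

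The cost is a few lines of SAP text, table labels, one footnote and a derivation that the supplied protocol already specifies. No new data are needed. The EoT rate may rise or fall, depending on which reading would have been programmed; the primary SVR12 rate does not change.

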11.4 Serious Adverse Event Collection Period

SAEs will be reported to AbbVie from the time the physician obtains the informed consent until 30 days or 5 half-lives following the intake of the last dose of physician-prescribed treatment.

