### 11.2 Adverse Events

Only treatment-emergent adverse events will be analyzed.

*Treatment-emergent AE* is any reported event that begins or worsens in severity after initiation of study drug through 30 days post-study drug dosing.

All analyzed AEs will be coded using the MedDRA version 20.0 (or further updating) and tabulated in the report with grouping by primary system organ class (SOC) and preferred term (PT).

The frequency of a specific AE occurrence will be presented by the proportion of patients with this AE emergence as well as the total number of episodes this AE for a diagnosis.

The following tables with descriptive statistics in accordance with section 7.1 will be presented:

- all AE / SAE;
- AE / SAE by severity;
- AE / SAE by relationship to the study drug.

Tables of AE/SAE by severity (relationship to the study drug) will be prepared using the following rules. Each SOC / PT category will include only the AEs with the highest severity (relationship to the drug) in each patient, while in the Total category all AEs of this patient will be considered. At the same time, each patient will be counted only once with highest severity (relationship to the study drug) in each SOC and each PT level as well as Total level.

Also all AEs will be presented in listings. Additional listings for unintended medication errors will be provided.

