**Table 4.2.1 Adverse events**  
The safety population  
Page X of X

| System organ class (SOC)
Preferred term (PT) | ABBVIE REGIMEN + RBV           |              | ABBVIE REGIMEN - RBV           |              | Overall
(N=XX)
n (%) /E |
|---|--------------------------------|--------------|--------------------------------|--------------|-------------------------------|
|   | 12 weeks
(N=XX)
n (%) /E | XX(XX.X) /XX | 12 weeks
(N=XX)
n (%) /E | XX(XX.X) /XX |                               |
| Total [1]                                       | XX(XX.X) /XX                   | XX(XX.X) /XX | XX(XX.X) /XX                   | XX(XX.X) /XX | XX(XX.X) /XX                  |
| System organ class 1                            | XX(XX.X) /XX                   | XX(XX.X) /XX | XX(XX.X) /XX                   | XX(XX.X) /XX | XX(XX.X) /XX                  |
| Preferred term A                                | XX(XX.X) /XX                   | XX(XX.X) /XX | XX(XX.X) /XX                   | XX(XX.X) /XX | XX(XX.X) /XX                  |
| Preferred term B                                | ...                            | ...          | ...                            | ...          | ...                           |
| ...   | ...                            | ...          | ...                            | ...          | ...                           |
| System organ class 2                            | ...                            | ...          | ...                            | ...          | ...                           |
| ...   | ...                            | ...          | ...                            | ...          | ...                           |
| ...   | ...                            | ...          | ...                            | ...          | ...                           |

N: the number of patients in the safety population.  
n: the number of patients who have AE with appropriate SOC/PT. Percentages are calculated as (100 x n/N) .  
E: the number of AE episodes, which have an appropriate SOC and/or PT.  
Patients with several AEs having the same SOC and PT are accounted only once for appropriate SOC and PT.  
[1] The Total line displays the number (n) and the proportion (%) of patients who have at least on AE as well as the total number of AE episodes in the study.  
The coding is carried out by the dictionary MedDRA v.20.1.  
The table does not include AEs that occurred prior to the first intake of the study drug.  

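### The SAP rule for adverse events with incomplete start dates ignores the end date, so an event known to have ended before the first dose can be counted as treatment-emergent

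*SAP*

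**What the plan says.** SAP 7.3 states that when the start of an adverse event is missing or incomplete, the rules of Table 7.1 "will be used for the classification of AEs for AEs of the study period and AEs, which occurred before the start of treatment". These are the only two classes. The tests are:

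- Day missing, month and year known: "AE will be classified as AE of the study period, if month and year" are not earlier than those of the first dose.
- Month missing, year known: the year is compared with the "year of the first study drug administration date".
- Year missing (three rows): "AE will be classified as AE of the study period", with no condition.

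SAP 11.2 analyses treatment-emergent events only, defined as "any reported event that begins or worsens in severity after initiation of study drug through 30 days post-study drug dosing". Protocol 9.7.7 uses the same window. The footnotes of the AE table shells (SAP 18, Tables 4.2.1, 4.3.1 and 4.4.1) state one filter: "The table does not include AEs that occurred prior to the first intake of the study drug".

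On collection, Protocol 11.4 has SAEs reported "from the time the physician obtains the informed consent" until 30 days or 5 half-lives after the last dose. Protocol Table 2 schedules AE reporting at baseline, and its footnote c ends tolerability documentation at post-treatment week 4. SAP 5.1 plans to show the stop day of events.

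**The concern.** Table 7.1 is the only rule for incomplete onset dates, and it is the step that separates events before treatment from events after it. It makes that decision without looking at the end date, which may already settle it. A pre-dose event with a vague start and a known pre-dose end is then labelled as if it arose on treatment.

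The rule also has no upper limit, so an event whose recorded month and year lie wholly more than 30 days after the last dose passes it as well.

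Tolerability is a stated secondary objective, and the treatment-emergent AE and SAE percentages are its main output. Under this rule, two events in the same clinical position can be counted differently solely because one has a complete date.

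**Working it through.** The plan gives no figure on this point, so there is none to reproduce. The check applies Table 7.1 to possible onset dates and compares the result with the SAP 11.2 window.

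**Inputs.** Window: first dose to last dose + 30 days (SAP 11.2). Tests: Table 7.1. Follow-up: 24 weeks after treatment (SAP 4.1). Enrolment target: 158 (SAP 4.2).

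**Assumptions**, since no patient dates are given: first dose 15 June 2016, a full 12-week course, and onset considered up to 365 days before the first dose.

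**Step 1, the window.** Last dose = 15 June + (84 − 1) days = 6 September 2016. Window end = 6 September + 30 days = 6 October 2016. Observation end = 15 June 2016 + (36 × 7 − 1) days = 21 February 2017.

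**Step 2, pre-dose onset days that pass Table 7.1.**

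| Missing part | First dose 1 Feb 2016 | 15 Jun 2016 | 31 Dec 2016 |
|---|---|---|---|
| Day | 0 | 14 | 30 |
| Month (year known) | 31 | 166 | 365 |
| Year | 365 | 365 | 365 |

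For 15 June: 1 to 14 June is 14 days, and 1 January to 14 June is 31 + 29 + 31 + 30 + 31 + 14 = 166 days. Passing these is acceptable where nothing else is known about the event.

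**Step 3, where the end date is known.** Take an event with start recorded as June 2016, day unknown, that ended on 10 June 2016. June 2016 is not earlier than June 2016, so Table 7.1 returns study period. The event was over five days before the first dose, so it cannot be one that "begins or worsens in severity after initiation of study drug through 30 days post-study drug dosing". With the start wholly missing, the result is the same with no test at all. With a complete start date of 8 June, the event would be pre-treatment.

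**Step 4, the upper limit.** Days from the end of the window to the end of follow-up = 24 × 7 − 30 = 138 (here 25 in October + 30 + 31 + 31 + 21). All 138 pass Table 7.1 under every missing-date pattern, and the same holds for the 24-week regimen. With only the day missing, a test on the earliest possible onset would remove 1 November to 21 February: 30 + 31 + 31 + 21 = 113 days. The 25 days in October would stay in by default. The 138 days are a ceiling set by follow-up, not by AE collection.

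**Step 5, effect per patient.** If the safety population is near 158, one patient is 1/158 = 0.63 percentage points of the overall rate. SAP 11.2 and the shells count each patient once per level, so this applies only to a patient with no other treatment-emergent event. The step is larger in the treatment-group columns, where denominators are smaller.

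**The case against.** The strongest reply is that Table 7.1 and SAP 11.2 can be applied in sequence. Table 7.1 never says that a study-period event is treatment-emergent. A programmer could pass events through it and then apply the 30-day limit wherever the known month and year suffice. This stands for the upper limit: a reader might infer that the SAP contradicts itself there, but the documents only leave unsaid how the two rules combine. It does not rescue the lower limit. Whether an event precedes treatment is exactly what Table 7.1 decides, and it returns the wrong class for an event with a known pre-dose end.

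A reader of Protocol 11.5 alone might also infer that non-serious reporting is open-ended, so that many late events enter. Protocol Table 2 does not support that. Footnote c stops tolerability documentation at post-treatment week 4, and the SVR12 and SVR24 visits carry pregnancy reporting only. With the SAE limit in Protocol 11.4, planned collection ends close to the end of the window. A small margin remains, from the half-life alternative for SAEs and from unsolicited reports.

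Finally, assigning uncertain onset to the treatment period is a usual conservative convention, and pre-existing illness should go to medical history (SAP 8.5). Both are fair and narrow the exposure. The defect is using the default when recorded dates already decide.

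**Conclusion.** The point holds for the end date and, more weakly, for the 30-day limit. As written, Table 7.1 can place an event known to have ended before the first dose among treatment-emergent events. An event dated wholly beyond 30 days after the last dose could also be kept, but few such events should be collected.

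The documents do not say how many events have incomplete dates, so no bias in the reported rates can be quantified. A reader might infer that every misclassified patient adds 0.63 points. That requires a safety population of about 158 and no other treatment-emergent event in that patient.

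Errors in placing onset go upward only. Worsening is a separate matter: Table 7.1 does not address events that began before the first dose and worsened later. SVR12 is unaffected.

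This rests on reading the study-period class as the route into the AE tables. That is an inference, but no other class or rule exists, and the footnotes exclude only pre-dose events. The collection limits come from the Protocol version supplied (3.0, country version 1.0), whereas the SAP cites version 4.0.

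**What to change.** Replace Table 7.1 with one rule. An adverse event with a partial or missing start date is treatment-emergent unless:

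1. its known end date is before the first dose; or
2. its latest possible start date is before the first dose and it did not worsen in severity after the first dose; or
3. its earliest possible start date is later than last dose + 30 days and it did not worsen within the window.

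Where the dates cannot decide, keep treatment-emergent as the default. Align the footnotes of the Table 4.2, 4.3 and 4.4 series with the full SAP 11.2 window, so that they state both limits.

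The cost is SAP wording and a few lines of programming, with no new data. SAP 2 allows revision before database soft lock; after that, the change should be explained in the study report.
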